Study protocol synopsis and statistical plan for “Mortality of Sepsis in Swedish Intensive Care Units 2008 – 2016”

Study protocol: 20th March 2018

Principal Investigator: [name], PhD

Investigators: [name], [name], [name].

Background

Accurate data on mortality in sepsis are important for several reasons, including allocation of resources, benchmarking, evaluation of interventions and for research purposes. Recent studies have indicated that the mortality of sepsis has decreased in the 21th century, although this view is not undisputed. Moreover, data on outcome beyond hospital discharge is limited. However, if mortality figures have improved, the cause of this is not entirely clear [1-3]. Preliminary data from Swedish intensive care units indicate that the mortality in sepsis may be relatively stable over the last decade in this setting. Therefore, we aim to study sepsis mortality from 2008 – 2016 in register data from Swedish intensive care units, and contrast this with mortality in other ICU patients. The specific research question is whether mortality has changed during this period. Primary outcomes are mortality at 30, 90 and 365 days after ICU admission. Secondary outcomes are hospital mortality and ICU and hospital length of stay.

Methods

Data are recovered from the Swedish Intensive Care Registry (SIR), a centrally administered nationwide collaboration where all general of intensive care units (ICU) in Sweden are members. We will include all adult (≥ 18 years) patients admitted to a general ICU between 1st of January 2008 and 18th of October 2016 (thoracic, neurosurgical, pediatric and burns ICUs are excluded). The cohort is divided in septic and non-septic patients. The former are identified by any of the International Classification of Diseases (ICD)-10 diagnoses R65.1, R57.2 and A41.9, which are used in the register to classify severe sepsis and septic shock. Data from SIR are linked with data from the national inpatient register of the Swedish Board of Health and Welfare (Socialstyrelsen), to recover chronic comorbidity data.

The septic and non-septic groups are characterized with regard to demographic factors; age, sex and type of treating hospital (regional, county, local), comorbidity; Charlson Comorbidity Index (CCI) and selected key diagnoses; diabetes, chronic heart or lung disease and malignancy, level of acute illness severity; Simplified Acute Physiology (SAPS)3 score, and selected interventions; invasive ventilation and renal replacement therapy. Also, ICU and hospital length of stay are described. These factors are described with appropriate statistics, i.e. mean and standard deviation (SD) or median and interquartile range (IQR) for parametric and nonparametric variables, or as proportions, and the beginning and end of the period are compared with t-test, u-test or χ^2 -test, respectively.

Proportional unadjusted mortality at hospital discharge, 30 days, 90 days and 365 days is also described in the whole population and in subgroups based on age, sex, type of treating hospital and severity of acute illness and chronic comorbidity.

The primary outcome measures; mortality at 30, 90 and 365 days after ICU admission, are further studied with logistic regression, adjusting for acute illness severity, comorbidity and demographic factors. Admission year is included as a regressor to assess the effect of time.

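### Do three unordered, overlapping primary mortality outcomes make the conclusion on change over time unreliable?

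*Protocol*

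**What the plan says.** The Background states a single question: "The specific research question is whether mortality has changed during this period". The outcomes follow directly: "Primary outcomes are mortality at 30, 90 and 365 days after ICU admission". Among the reasons for the study is that "data on outcome beyond hospital discharge is limited".

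The last analysis paragraph of the Methods returns to the same three as primary and says that they "mortality at 30, 90 and 365 days after ICU admission, are further studied with logistic regression", adjusted for acute severity, comorbidity and demographic factors. The test of change is the year term: "Admission year is included as a regressor to assess the effect of time".

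The paragraph before it has crude mortality described at hospital discharge and at all three time points, overall and in subgroups.

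The protocol states no significance level, no lead time point, no testing order and no rule for discordant results. It does not say that a trend at any one time point suffices for a claim of change. Non-septic patients enter as a contrast to the septic group, and the text does not say that the regressions form separate primary tests in each group.

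**The concern.** Two things look wrong.

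**Multiplicity.** One question is put to three primary tests without priority. A trend at 90 days but not at 30 or 365 could be written up as change or as stability without departing from the plan. If any one result is enough, the false-positive chance exceeds the level of each single test. The document calls itself a statistical plan in its title ("Study protocol synopsis and statistical plan for"), so one might expect the matter to be settled here.

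**Overlap.** All three outcomes count from ICU admission, so a death by day 30 is counted again at 90 and 365 days. The protocol notes that outcome after discharge is poorly documented, yet a 365-day model mixes early with late deaths. At stake would be an early improvement read as better long-term recovery, or a late worsening masked by an early gain.

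**Working it through.** The protocol gives no error rate, significance level or mortality rate, so there is no stated figure to reproduce. What follows rests on assumptions.

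**1. Error rate**

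Inputs: three outcomes (protocol); 5% two-sided per test (assumed); mortality at 30/90/365 days (assumed, over a range).

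- Upper references: independent tests, 1 − 0.95³ = 14.3%; Bonferroni bound, 3 × 5% = 15%.
- Nested outcomes with cumulative risks p₁ < p₂ have null correlation √[p₁(1 − p₂) / (p₂(1 − p₁))]. At 25/32% this is √(0.25 × 0.68 / (0.32 × 0.75)) = 0.84.
- The last two columns come from trivariate-normal simulation with these correlations.

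| Assumed 30/90/365-day mortality | Correlations (30–90, 30–365, 90–365) | At least one of three significant | All three significant |
|---|---|---|---|
| 15/18/25% | 0.90, 0.73, 0.81 | 9.5% | 1.5% |
| 25/32/42% | 0.84, 0.68, 0.81 | 10.0% | 1.2% |
| 30/37/47% | 0.85, 0.70, 0.81 | 9.8% | 1.3% |

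More extreme assumptions move the any-of-three figure from 8.3% (30/33/37%) to 12.0% (10/20/40%). A direct simulation of logistic regressions on year at 30/36/44%, with 4,000 patients and 1,500 runs, gave 10.3%, against 9.4% from the normal approximation.

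The doubling is therefore correct under an any-of-three rule. Under an all-three rule the error is well below 5%. The protocol contains neither rule.

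Counting septic and non-septic patients as two families of primary tests would raise the total further. The protocol does not support that count: a chance trend among the comparators is not a false finding about sepsis.

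**2. Overlap**

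365-day mortality = p₃₀ + (1 − p₃₀) × later mortality among day-30 survivors. All inputs are assumed.

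- Start: 0.30 + 0.70 × 0.22 = 45.4%.
- 30-day mortality falls to 26%, later mortality unchanged: 0.26 + 0.74 × 0.22 = 42.3%. Odds ratio (0.4228/0.5772) / (0.454/0.546) = 0.88.
- 30-day mortality falls to 26%, later mortality rises to 26%: 0.26 + 0.74 × 0.26 = 45.2%, practically flat.

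In a simulation with a true trend in 30-day mortality only (log-odds −0.02 per year), the 365-day trend was significant in 70% of runs with 20,000 patients and 94% with 40,000. The trend in days 91–365 among day-90 survivors was significant in about 4%, its null rate. A one-year trend can thus be pure carry-over.

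**3. What a reader of the planned results would see**

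- Second case: a one-year fall from 45.4% to 42.3%. That is true, and the 30-day result shows the same fall.
- Third case: 30-day mortality down from 30% to 26% beside one-year mortality flat at about 45%. The divergence reveals the late worsening. It would be hidden only if 365 days were reported alone, which is not what the Methods describe.

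**The case for a change.** The strongest case for a change is that leaving the rule open is itself the defect. The document fixes three equal primaries and calls itself a statistical plan, and the Background already reports preliminary data suggesting stable mortality. A written order or lead time point would cost a sentence and remove any room to choose after seeing the results. Separate models for days 31–90 and 91–365 among survivors need no new data and would address post-acute mortality directly.

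Part of this stands. No order is written, and the 365-day outcome cannot separate late from early deaths. But the remedies are not clear gains:

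- Testing 30 days first and passing to 365 only on success subordinates the long-term outcome that the Background describes as poorly documented. If 30-day mortality is stable, as the preliminary data suggest, the one-year result could never be confirmatory.
- Putting the septic group first would leave the contrast group untested exactly when sepsis mortality is stable.
- Models among survivors condition on an outcome. If early survival improves, later survivors may be sicker, and the year term would carry that shift in case mix.
- Such models add tests. They do not correct an estimate that the plan gets wrong.

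**Conclusion.** The description is accurate: three nested primary outcomes, no order, one question. The consequences are conditional or overstated.

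- **False-claim rate.** It is about 9.5–10% only if each test is at 5% and any one suffices. Both are assumptions, as are the mortality rates. Requiring agreement gives about 1.2–1.5% over the same rates.
- **Long-term mortality.** Cumulative 365-day mortality validly answers whether one-year mortality changed. What it does not do is isolate post-acute deaths, and the protocol does not claim that it does.
- **Masking.** With all time points reported together, divergent early and late trends would be visible.

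This is an observational trend study with three closely related outcomes, all of them to be reported. The missing rule for discordant results is a gap that analysts fill by presenting the three estimates together and describing the pattern. Whether to impose a formal hierarchy is a trade-off on which reasonable statisticians differ. Followed as written, the plan yields sound estimates at each time point, so no change is called for.

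### ICU and hospital length of stay are secondary outcomes, yet their change over 2008–2016 is tested only by comparing the first part of the period with the last, so the course through the middle years is not seen

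*Protocol*

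**What the plan says.** The outcomes are set out in the Background section of the protocol: "Secondary outcomes are hospital mortality and ICU and hospital length of stay". The Methods section defines the cohort as all adult "patients admitted to a general ICU between 1st of January 2008 and 18th of October 2016", so individual admissions are available for eight full calendar years and most of a ninth.

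The paragraph in Methods on the characteristics of the septic and non-septic groups lists demographic factors, comorbidity, acute severity and interventions, and then adds: "Also, ICU and hospital length of stay are described". The next sentence refers back to all these factors, gives the summary statistics, and states the test of change: "the beginning and end of the period are compared with t-test, u-test", with a chi-squared test as the third option. Neither window is dated.

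The last paragraph of Methods gives the regression analysis. It covers the primary outcomes only: "mortality at 30, 90 and 365 days after ICU admission, are further studied with logistic regression". The time effect belongs to that model: "Admission year is included as a regressor to assess the effect of time". No other analysis of length of stay over time is stated.

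**The concern.** The sentence that sets the two-group tests directly follows the one on length of stay, so the tests apply to it. For two named outcomes, the plan's only stated evidence of change over almost nine years is therefore a contrast of two blocks of time. With narrow windows most admissions do not enter the test. With wide windows they enter, but the years within each block are pooled. In neither case does the analysis show whether a change was gradual, abrupt, or reversed partway.

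This is a choice of method that the document makes, and its title calls it a statistical plan as well as a protocol synopsis. The plan already has the better tool, admission year as a regressor, but does not apply it here. At stake is how informative the length-of-stay result will be. The answer on mortality is not at stake.

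**Working it through.** The plan states no sample size, effect or power for length of stay, so there is no figure of its own to reproduce. The calculation below is an illustration.

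**Inputs.** The cohort dates are from Methods ("between 1st of January 2008 and 18th of October 2016"). Days per calendar year, 2008 to 2016: 366, 365, 365, 365, 366, 365, 365, 365, 292; total 3214. Assumptions: admissions proportional to days, constant variance, linear change on the analysed scale, two-sided alpha 0.05. The windows are not dated, so one, two and three calendar years at each end are shown.

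**Information on a linear slope**
- Trend over all years: Sxx = Σ n(t − t̄)². With t̄ = 2011.908, Sxx = 20,721.
- Contrast of two windows A and B: (t_B − t_A)² / (1/n_A + 1/n_B), where t_A and t_B are the mean years of the windows.
- Efficiency = contrast / trend.

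| Windows | n_A, n_B (days) | t_B − t_A | Contrast information | Efficiency | Share of admissions used |
|---|---|---|---|---|---|
| One year | 366, 292 | 8.000 | 10,395 | 0.502 | 658/3214 = 20% |
| Two years | 731, 657 | 6.945 | 16,690 | 0.805 | 1388/3214 = 43% |
| Three years | 1096, 1022 | 5.929 | 18,594 | 0.897 | 2118/3214 = 66% |

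The inverses, 1.99, 1.24 and 1.11, are the factors by which admissions would have to rise for the contrast to match the trend.

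**What this means for power.** Power of the contrast = Φ((1.96 + z_p)·√efficiency − 1.96), where p is the power of the trend test. Both values of p below are hypothetical.
- p = 80%: Φ(2.802·√efficiency − 1.96) = 51%, 71%, 76%.
- p = 99%: 86%, 97%, 98%.

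So the loss of power shrinks as the register becomes large relative to the change of interest.

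**What each method sees of a curved course.** Take y = 1 − ((t − peak)/4)², which has height 1 at its peak.

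| Peak | Contrast, one / two / three years | Linear trend over all years, slope × 8 years |
|---|---|---|
| 2012 | 0.00 / 0.02 / 0.03 | 0.07 |
| 2011 | −1.00 / −0.84 / −0.71 | −0.93 |
| 2013 | +1.00 / +0.89 / +0.77 | +1.07 |

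A rise and fall centred on 2012 is almost invisible to the contrast and to the straight line alike. Off-centre peaks show up in both, but only as a net difference. Only a fit with year as a category recovers the shape.

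**The case against.** The strongest reply is that length of stay is handled descriptively, and consistently so. The research question concerns mortality alone. Hospital mortality, the other secondary outcome, is also only described, and modelling is reserved for the primary outcomes. A two-sample test is valid, no decision hangs on it, and the same contrast is unobjectionable for the case-mix variables in the same sentence. Most of this stands, and it is why the point ranks low. It does not remove the point: length of stay is a named outcome, the plan attaches a hypothesis test to it, and a fuller analysis of data already held costs little.

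A second reply concerns size. The 50% figure needs single-year windows, which the document does not specify, and two- or three-year windows keep 81% to 90%. In a nationwide register even the larger loss may not change a conclusion. That also stands, so loss of power is not the main argument.

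A third reply is that a linear trend would miss a symmetric rise and fall too. This is correct, and it shapes the fix.

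A reader might go further and infer that the undated windows let the analyst choose the years that give a significant result, or that the verdict will turn on the windows chosen. The document does not support this. Nothing in it suggests such selection, the missing dates are a detail that can be settled elsewhere, and dating the windows would remove both worries.

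**Conclusion.** The point holds in a limited form. For ICU and hospital length of stay, the stated two-group contrast makes poorer use of the 2008–2016 data than an analysis by admission year, and it cannot show what happened between the two ends. Under a linear change, with admissions proportional to days, it keeps about 50%, 81% or 90% of the information in an all-years trend for one-, two- or three-year windows. Whether that loss matters depends on a sample size that the document does not give. The failure to show the middle years does not depend on sample size.

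This does not call the study's main conclusion into question. The mortality models use all years and are not touched, and the descriptive case-mix comparisons are not part of the point. It is a cheap improvement, for the investigators to consider.

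**What to change.** Add a sentence or two to Methods: ICU and hospital length of stay will be analysed by admission year over all admissions, separately in septic and non-septic patients, with a method suited to skewed data (for example a log-scale model or quantile regression). Year will be fitted as a linear term and also as a category, the latter because a straight line alone would miss a symmetric rise and fall.

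The cost is four routine models (2 outcomes × 2 groups), each fitted in two forms, so eight fits on data already held. The downside is slightly more analysis work and a longer table. The mortality models need no change.

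### The planned logistic regression makes no allowance for ICU clustering, so the interval for the admission-year effect is too narrow if mortality within ICUs fluctuates from year to year; this matters mainly for the non-septic contrast

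*Protocol*

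**What the plan says.** The Background section sets the aim: "The specific research question is whether mortality has changed during this period", in sepsis and in contrast with other ICU patients. It adds that preliminary data suggest "the mortality in sepsis may be relatively stable over the last decade in this setting".

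The Methods section takes "patients admitted to a general ICU between 1st of January 2008 and 18th of October 2016" from a registry to which all general ICUs in the country belong, and states that "The cohort is divided in septic and non-septic patients". The primary outcomes "are further studied with logistic regression, adjusting for acute illness severity, comorbidity and demographic factors". For the time trend: "Admission year is included as a regressor to assess the effect of time".

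The only variable that describes the centre is "type of treating hospital (regional, county, local"), listed among the demographic factors. No ICU term, random effect or variance method for correlated data is named. The title calls the document a statistical plan as well as a protocol synopsis.

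**The concern.** The admission-year coefficient and its interval carry the answer to the research question. Ordinary logistic regression computes that interval as if patients were independent once the covariates are known. Patients treated in the same ICU in the same year share staffing, local practice, admission policy and coding habits. Where these vary over time within an ICU, the year slope is less certain than the model reports.

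If the true trend is small, as the preliminary data suggest for sepsis, an interval that is too narrow can decide whether a change is declared. The distortion grows with the number of patients per ICU-year. It can therefore differ between the septic and non-septic groups, whose contrast is part of the aim.

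**Working it through.** The protocol states no sample size, event count, ICU count or variance component, so there is no figure of its own to reproduce.

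**Inputs.** From the protocol: recruitment from 1 January 2008 to 18 October 2016. Assumed: K = 50-80 ICUs of equal size; septic N = 25,000 with mortality m = 0.30; non-septic N = 200,000 with m = 0.16; independent ICU-by-year shifts with SD s on the log-odds scale.

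**Spread of admission year.** 2016 contributes 292/366 = 0.80 of a year, so the period is 8.80 years. Years 0-7 get weight 1 and year 8 gets weight 0.80. The weighted variance of year is 6.44.

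**Model-based standard error per year**, 1/√(N·m·(1−m)·6.44):
- septic: 1/√(25,000 × 0.21 × 6.44) = 0.00544
- non-septic: 1/√(200,000 × 0.1344 × 6.44) = 0.00240

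**True standard error.** The ICU-by-year shifts add s²/(K × 59.5) to the variance of the slope. With w the year weights and d the distance from the mean year, 59.5 = (Σwd²)²/Σw²d² = 56.7²/54.0.

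Worked case, s = 0.2 and K = 50: added variance 0.04/(50 × 59.5) = 0.00001345.
- septic: √(1 + 0.00001345/0.00544²) = 1.21
- non-septic: √(1 + 0.00001345/0.00240²) = 1.82

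The actual error of a nominal 5% test is 2 × (1 − Φ(1.96/ratio)). Ranges below run over K = 80 to 50.

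| ICU-by-year SD | Septic SE ratio | Septic error | Non-septic SE ratio | Non-septic error |
|---|---|---|---|---|
| 0.05 | 1.01 | 5.2-5.3% | 1.04-1.07 | 6.1-6.7% |
| 0.1 | 1.03-1.06 | 5.8-6.3% | 1.17-1.26 | 9.3-11.9% |
| 0.2 | 1.13-1.21 | 8.4-10.4% | 1.57-1.82 | 21-28% |

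**Sensitivity to group size.** With K = 65 and SD 0.1 to 0.2, a septic N of 10,000 gives ratios of 1.02-1.07, and 40,000 gives 1.07-1.25.

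**Simulation with no true trend.**
- 65 ICUs, 2,000 runs: the plain model rejected in 5.3% (septic) and 11.1% (non-septic) of runs at SD 0.1, and in 9.1% and 28.8% at SD 0.2. ICU-cluster-robust standard errors gave about 5%.
- 50-80 ICUs of unequal size, 3,000 runs per setting: the plain model gave 6.4-6.9% (septic) and 10.7-13.5% (non-septic) at SD 0.1, and 8.5-13.1% and 24.8-33.7% at SD 0.2. Cluster-robust errors gave 5.1-5.8% throughout.
- 60 ICUs with 60 patients per ICU-year, 30% mortality, 1,000 runs: constant ICU differences alone (SD 0.3) gave 96.6% coverage of the plain 95% interval, so no narrowing. Adding ICU-by-year SD 0.1 gave 95.2%. SD 0.2 gave 90.4%, restored to 95.0% by cluster-robust errors.

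**The case against.** **The variance method may simply be unstated.** The text says logistic regression and names no standard error, and cluster-robust errors are compatible with it. This is fair: the plan omits the allowance, it does not reject it. But the document calls itself the statistical plan and fixes the model, its covariates and the time term. The method that decides the width of the key interval belongs beside them.

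**For sepsis the effect may be nothing.** This stands in large part. Every driving input is assumed. At SD 0.1 the simulated septic error ran from 4.8% to 6.9% depending on the set-up. The large figures need an SD near 0.2, or the non-septic group at an assumed 200,000 patients; the protocol gives no group sizes.

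**All general ICUs belong to the registry, so they may be the whole target.** In that case, and if ICUs have lasting different trends, cluster-robust intervals are too wide: with a slope SD of 0.03 the error falls to 1.8% (septic) and 0.1% (non-septic). This is a real cost. It does not remove the narrowing when the variation is year-to-year fluctuation.

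**Stronger readings that a reader might infer.**
- That any difference between ICUs invalidates the interval. Constant differences with a stable patient mix do not.
- That deaths are counted twice. The text speaks of patients, and one row per patient is the natural reading. Double counting would need admissions as rows, which the text does not say.
- That the missing index-admission rule could by itself create a sizeable trend. With no true trend, a first-admission rule gives a spurious odds ratio over 8 years of 0.99-1.00 if 5-8% of patients have two admissions, and 0.97-1.00 if 13-20% do. One septic standard error over 8 years is 8 × 0.00544 = 0.044 in log odds ratio. Values as low as 0.87 need a last-admission rule with 13-20% readmitted, and the protocol states neither.

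**Conclusion.** The point holds as a conditional one. The planned model does not allow for ICU clustering, and its interval for the year effect is too narrow if mortality within ICUs fluctuates between years. Under the assumed sizes this is negligible for the septic trend at an ICU-by-year SD of 0.1 or below. It becomes material for sepsis near 0.2. For the non-septic group it already matters at 0.1. The documents do not support saying that the sepsis result will be wrong, since they give no information on the size of the fluctuation. The change is worth making because it is cheap, and because the non-septic trend is the stated comparator.

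The index admission is a secondary clarification, not a finding in itself. Admission year, SAPS3, sepsis status and the clock behind "Primary outcomes are mortality at 30, 90 and 365 days after ICU admission" belong to an admission, and the text does not say which one represents a patient admitted more than once.

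**What to change.** Keep the same logistic model and report ICU-cluster-robust standard errors for the year effect in both the septic and the non-septic analysis. First confirm that the extract carries an ICU identifier.

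Cost: one sentence and one option in the model fit. In simulation with unequal ICU sizes, septic intervals become 1.01 times as wide with no ICU-by-year variation, 1.05-1.09 times at SD 0.1 and 1.18-1.27 times at SD 0.2. The intervals are conservative if ICUs have lasting different trends and only the observed ICUs are the target. They give no protection against shocks shared by all ICUs in a year: with a simulated common year SD of 0.05, coverage was 76% plain and 74% cluster-robust.

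As a clarification, state which admission supplies year, SAPS3, sepsis status, hospital type and the outcome clock, for example the first in the period with transfers between ICUs joined into one episode. This needs a patient identifier. Such a rule classes patients whose sepsis occurs only at a later admission as non-septic, and drops readmission records. With no look-back before 2008 it can also create a small trend (illustrative odds ratio 0.97-1.00 over 8 years).

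A sensitivity analysis of admissions from 1 January 2009 with no ICU admission in the preceding 365 days removes that trend, with a standard error 1.20 times larger. If it is used, state that patients may re-enter after 365 clear days, so it is not limited to one admission per patient.
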